10.5 Visit Windows

Windows for timed PK blood sample collections are presented in Table 7. PK samples collected outside of the pre-specified windows will be documented as protocol deviations. Since actual times are to be used for the PK analysis, deviations will be reflected in the analysis unless indicated otherwise upon review of the data.

Table 8: Acceptable PK Visit Windows

Elapsed Time	Accepted Window
Predose	No window specified
> 0 hour to \leq 30 minutes	\pm 1 minute
> 30 minutes to \leq 4 hours	\pm 2 minutes
> 4 hours to \leq 12 hours	\pm 5 minutes
> 12 hours to \leq 24 hours	\pm 10 minutes
> 24 hours to \leq 72 hours	\pm 2 hours
> 72 hours	\pm 4 hours

10.6 Pharmacokinetic Statistical Methodology

All tables, figures, and listings (TFLs), when appropriate, will be stratified by treatment.

10.6.1 Summary Statistics

Summary statistics of the individual concentration data and derived parameters will be calculated with Phoenix® WinNonlin® for the PK population. Summary statistics will be calculated for concentration at each individual time point and for all PK parameters.

C_{trough} will be displayed graphically and summarized descriptively by day to assess for steady state.

Appropriate dose-normalized PK parameters ($C_{\text{max, ss}}$, $C_{12, \text{ss}}$, $C_{24, \text{ss}}$, and $AUC_{0-\text{TAU, ss}}$, when appropriate) will be assessed graphically for dose-proportionality. Concentration data will be summarized by group using the following statistics: number of observations (n), arithmetic mean (mean), SD, min, median, max, and CV%. The PK parameters will be summarized using these same statistics, as well as geometric mean and geometric mean CV%.

No comparison between fed and fast state will be provided.

10.6.2 Dose Proportionality

Natural log-transformed PK parameters ($C_{\text{max, ss}}$, $C_{12, \text{ss}}$, $C_{24, \text{ss}}$, and $AUC_{0-\text{TAU, ss}}$) will be assessed statistically for proportionality. Proportionality analysis will be done using a power model. The power model is defined as:

$$\ln(\text{PK parameter}) = \alpha + \beta \cdot \ln(\text{Dose}) + \varepsilon$$

where α is the intercept, β is the slope and ε is the error term. A linear model with ln-transformed dose as a continuous effect will be fitted. A point estimate and a 90% confidence interval will be derived for the slope (β).

The parameter can be considered to be dose-proportional if the 90% CIs for the slope coefficient that include 1 will suggest evidence of dose proportionality.

Dose proportionality may be assessed within different dose ranges if deemed appropriate with at least three doses.

Otherwise, if there are only two cohorts completed, Statistical inference will be based on a bioequivalence approach for a parallel group design and expressing the relative difference as a geometric mean ratio and 90% CI using ANOVA model based on dose normalized PK parameters.

No comparison between fed and fast state will be provided.

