| Safety Meetings for Dose Adjustments: | Following completion of each cohort, a Safety Review Committee (SRC) will review all available safety and PK data (through Day 15, 24 hours post last dose) to evaluate progression to the next dose cohort. The SRC will be comprised of the Investigator (or designee) at the Investigational site, the Study Manager and the Sponsor's medical personnel at a minimum. Additional advisors could be invited as required. During the study, each prescheduled cohort may be conducted at the dose outlined in the protocol or may be adjusted to a lower or equivalent dose, on the basis of safety, tolerability, and PK data (if available) reported in the previous cohorts. An optional dose titration cohort may be added. |
| Study Population: | Healthy adult subjects |

| | |
|------------------------------------|---|
| Planned Number of Subjects: | A maximum of 32 subjects will be included in the study. Each of the 4 cohorts will include 8 subjects. |
| Bioanalysis: | TMP-301, caffeine and paraxanthine plasma concentrations will be measured by validated bioanalytical methods. |
| Pharmacokinetic Analysis: | The PK analysis will be fully detailed in a Statistical Analysis Plan (SAP). |
| Statistical Analysis: | The statistical analysis will be fully detailed in a SAP. |

STUDY ADMINISTRATIVE STRUCTURE

Commercially Confidential Information

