3. STUDY DESIGN

3.1. Adaptive Features and Risk Management of Study Design

The rationale of having the following adaptive features is based on the hypothesis-forming approach of this clinical trial. Dose escalation or de-escalation, including titration, categories will be adapted as follows:

Table 1: Adaptive Features and Boundaries

| Adaptive study design category | Adaptive Features | Boundaries |
|--------------------------------|--|---|
| Dose adjustment | Doses for the subsequent cohorts will be determined/adapted based on tolerability, and PK data (if data through Day 15 permits and is available) collected in previous cohort. | Doses are intended to escalate; however, they may be adjusted to a lower, an equivalent dose or a higher dose as per the adaptive features. For any cohort the mean maximum systemic exposure should not exceed or be predicted to exceed an AUC_{0-24} of 16,200 $h.ng/mL$ at steady state and/or a maximum serum concentration predicted to exceed a C_{max} of 783 ng/mL^a |
| The number of MAD cohorts | The quantity of MAD cohorts may be adapted | The maximal number of different dose level cohorts will be 4. |
| Dose Titration | Dose titration may be added in this study based on interim safety data reviews and tolerability to the study drug. | Based on safety/tolerability findings in any of the previous cohorts, a 14 day dose titration cohort (7 days at initial dose + 7 days at higher dose) may be added. |
| Dosing with meals | Dosing may be done in a fasted or fed state. | At the selected dose level, the predicted effect of food on exposure will not exceed the thresholds described above. |

Abbreviations: MAD = multiple ascending dose; PK = Pharmacokinetics.

^aExposure limits were based on 28D Rat NOAEL exposures, with an additional 10x safety factor.

Commercially Confidential Information

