3 STUDY DESIGN

3.1 General Description

This study will be a randomized, double-blind, placebo -controlled, fixed -sequence, MAD study. The study will be conducted in a single clinical research unit (CRU). The study will consist of up to 4 cohorts. Each cohort will consist of 8 subjects (6:2 for active: placebo), for a maximum total sample size of approximately 32 subjects. Subjects will only participate in 1 cohort.

Screening will occur within approximately 28 days prior to the first scheduled study drug administration. Screening data will be reviewed to determine subject eligibility. Subjects who meet all inclusion criteria and none of the exclusion criteria and who consent to participation will be admitted to the CRU for baseline evaluations prior to dosing. All baseline safety results should be available prior to the first study drug administration.

In cohort 2, subjects will be fasted overnight for 10 hours prior to the morning dose, followed by a 2 hour fast. Subjects were fasted for 2 hours prior to dosing and 2 hours following the evening dose for the cohort 1 (50 mg bid). If dosing in a fed condition is selected for cohort 3 or 4, subjects will be fasted overnight for approximately 9 hours, then given breakfast followed by study treatment dosing 30 minutes after initiation of breakfast.

Each subject will be randomly assigned to 1 of the following cohorts:

- Cohort 1:
 - Group 1 (6 subjects): 50 mg of TMP-301 bid
 - Group 2 (2 subjects): placebo (matching TMP-301) bid

- Cohort 2:
 - Group 3 (6 subjects): 50 mg of TMP-301 qd
 - Group 4 (2 subjects): placebo (matching TMP-301) qd

- Cohort 3:
 - Group 5 (6 subjects): Dose regimen of TMP-301 to be determined
 - Group 6 (2 subjects): placebo (matching TMP-301)

- Cohort 4:
 - Group 7 (6 subjects): Dose regimen of TMP-301 to be determined
 - Group 8 (2 subjects): placebo (matching TMP-301)

Safety will be assessed and blood samples for PK will be collected throughout confinement. Subjects will be discharged from the CRU on Day 18. Subjects will return to the CRU on Day 25 for a follow-up visit and End-of-Study (EOS) procedures.

Caffeine (100 mg) will be included as probe CYP1A2 substrate in cohort 2 and subsequent cohorts. Ratio of plasma paraxanthine/caffeine will be determined in a blood sample 4 hours after administration of caffeine at baseline (Day-1) and on day 14.

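### SAP 10.6.2 regresses steady-state concentrations on an undefined Dose with no BID/QD term, and AR_C24 compares unlike times after dose in the BID cohort

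*SAP*

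**What the plan says.** SAP 10.6.2 applies a power model, ln(parameter) = α + β·ln(Dose) + ε, to Cmax,ss, C12,ss, C24,ss and AUC0-TAU,ss: "A linear model with ln-transformed dose as a continuous effect will be fitted". Proportionality is judged from the 90% CI of the slope: "The parameter can be considered to be dose-proportional if the 90% CIs for the slope coefficient that include 1". Subsetting is optional and by dose range only: "Dose proportionality may be assessed within different dose ranges if deemed appropriate with at least three doses". There is one exception to the model: "Otherwise, if there are only two cohorts completed, Statistical inference will be based on a bioequivalence approach for a parallel group design", which uses dose-normalised parameters and a geometric mean ratio with 90% CI. The normalising dose is not defined and no acceptance limits are given for the ratio.

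The two fixed active arms in SAP 3.1 are "Group 1 (6 subjects): 50 mg of TMP-301 bid" and "Group 3 (6 subjects): 50 mg of TMP-301 qd". Later doses are open: the protocol synopsis says a cohort "may be adjusted to a lower or equivalent dose, on the basis of safety, tolerability, and PK data", and Protocol 3.1, Table 1 says of the doses that "they may be adjusted to a lower, an equivalent dose or a higher dose as per the adaptive features". Protocol 5.3 makes cohorts 3 and 4 once daily, whereas Protocol Table 2 leaves their dose and regimen to be determined.

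SAP Table 7 labels the AUC accumulation ratios by regimen but gives AR_C24 for all cohorts, as C24,ss over the Day 1 C24, which is the Day 2 trough. In BID cohorts the Day 14 evening dose is not given (Protocol Table 3, footnote i).

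**The concern.** At the same capsule strength, twice-daily dosing leaves more drug on board than once-daily dosing. That raises peak and trough concentrations through regimen, not through any departure from proportionality. A model whose only regressor is ln(Dose) must put this difference into the slope or the residual. A proportional drug can then be reported as non-proportional. The reverse is also possible: with four cohorts on dose per administration, a true slope above 1 is pulled down towards 1.

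If the study stops after cohorts 1 and 2, a BID versus QD contrast would appear under a dose-proportionality heading. For AR_C24 in BID, a reader could see a value below 1 and conclude that the drug does not accumulate.

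**Working it through.** **Inputs.** From the documents: six actives per cohort; 50 mg BID (2 × 13 + 1 = 27 doses, matching the stated 27) and 50 mg QD (14 doses); 90% CI. Assumed, because the PK sections are redacted and later doses are undecided: linear one-compartment kinetics, half-life 4 to 48 h, between-subject CV 30%. The dose multiples are arithmetic illustrations only. The plan gives no figure of its own to reproduce.

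**1. BID/QD ratio.** Let x = 2^(−12/half-life), the fraction left after 12 h. At steady state (bolus form) C12,ss is x/(1−x) in BID and x/(1−x²) in QD. C24,ss is x²/(1−x) and x²/(1−x²). Both ratios equal 1+x, and Cmax,ss is close to that. AUC0-TAU,ss per administration has ratio 1.00.

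**2. Expected slope when the true slope is 1.** Let L = ln(1+x), and measure ln(Dose) from 50 mg in units of ln 2.
- Three cohorts, Dose per administration, later QD at twice the dose: positions (0, 0, 1), responses (L, 0, ln 2). Least squares gives 1 − L/(2 ln 2). At 12 h: 1 − 0.405/1.386 = 0.71.
- Same, later QD at half the dose: 1 + L/(2 ln 2). A later BID cohort at twice the dose gives the same value.
- Daily dose, later QD at twice or half the dose: positions (1, 0, 1) or (1, 0, −1). Both give 1/2 + L/(2 ln 2).
- Four cohorts, QD multiples 1, 2, 4. Per administration: 1 − (3/11)·L/ln 2, i.e. 0.95 to 0.76. Daily dose: cohort 1 sits at the mean of ln(Dose), so the slope is 1.00.

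| Half-life (h) | 4 | 8 | 12 | 24 | 48 |
|---|---|---|---|---|---|
| BID/QD ratio, 1+x | 1.13 | 1.35 | 1.50 | 1.71 | 1.84 |
| Slope, per administration, later QD ×2 | 0.92 | 0.78 | 0.71 | 0.61 | 0.56 |
| Slope, per administration, later QD ×½ | 1.08 | 1.22 | 1.29 | 1.39 | 1.44 |
| Slope, daily dose, either case | 0.58 | 0.72 | 0.79 | 0.89 | 0.94 |
| 90% CI excludes 1, per administration, CV 30% | 12% | 21% | 28% | 36% | 41% |
| AR_C24 in BID, x/(1−x²) | 0.13 | 0.40 | 0.67 | 1.41 | 2.87 |
| Matched trough ratio, 1/(1−x²) | 1.02 | 1.14 | 1.33 | 2.00 | 3.41 |

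The exclusion rates come from at least 100,000 simulated log-normal trials per setting. With four cohorts they are 13% to 55% per administration and 3% to 10% on daily dose. With a regimen term the mean slope is 1.00 and the rate 10% in every case with later QD cohorts, if food state is the same throughout.

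**3. AUC0-TAU,ss.** Per administration the slope is 1. On daily dose the three-cohort slope is 0.50.

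**4. Cohorts 1 and 2 only.** Per administration the contrast is 50 against 50, so there is no dose difference. By daily dose it is 100 against 50, which coincides with regimen. The expected concentration ratio for a linear drug is 1+x (1.13 to 1.84) or, normalised by daily dose, (1+x)/2 (0.56 to 0.92). AUC0-TAU,ss normalised per administration has expected ratio 1.00 and is in effect a CL/F comparison.

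**5. AR_C24 in BID.** The numerator is 24 h after the last dose, x²/(1−x). The denominator, the Day 2 trough, follows two doses and is 12 h after the second, x + x². The quotient is x/(1−x²). A matched ratio (Day 14 predose over Day 2 predose) is 1/(1−x²). AR_C24 is below 1 when x < 0.618, i.e. half-life under about 17.3 h. Simulating the 27 actual doses at 48 h gives 2.84 against 3.38, because steady state is not quite reached.

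**The case against.** The strongest reply is that the bias is neither fixed nor known. Half-life, variability and later doses are redacted or undecided. On daily dose with QD multiples 1, 2 and 4 the slope is exactly 1.00. Even per administration, most three-cohort intervals at CV 30% still include 1. The outputs are exploratory, and matched BID accumulation is already available from AR_C12 and AR_AUC0-12. All of this stands. It limits severity and rules out an unconditional statement of direction, but it does not supply a definition of Dose under which the concentration parameters fit.

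Two passages might be offered as a cure. Stratification by treatment (SAP 10.6) concerns outputs, and the phrase about appropriateness in 10.6.1 concerns graphs. Neither alters the model.

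A reader might infer more than the documents support:
- That the slope is biased below 1, or not estimable when all doses are equal. Both depend on Dose meaning dose per administration. The CL/F definition in Table 7 supports that reading, but 10.6.2 does not state it.
- That three cohorts with only two QD doses have no named analysis. The power model is the default, and the only stated departure is for two completed cohorts.
- That the fallback tells us nothing. This is too broad for AUC0-TAU,ss.
- That the fallback would often reject proportionality falsely. The SAP gives no decision rule for that ratio.

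**Conclusion.** The point holds in this form. For Cmax,ss, C12,ss and C24,ss the model in SAP 10.6.2 mixes regimen with dose, and neither meaning of Dose removes this. Under linear one-compartment kinetics, half-lives of 4 to 48 h, CV 30% and one later QD cohort, the slope for a proportional drug is 0.92 to 0.56 or 1.08 to 1.44 per administration (later dose doubled or halved), and 0.58 to 0.94 on daily dose. AUC0-TAU,ss is sound if Dose is per administration.

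If only cohorts 1 and 2 complete, the concentration ratios measure BID versus QD accumulation. The AUC0-TAU,ss ratio, normalised per administration, compares CL/F at 100 and 50 mg/day with dose and regimen confounded. AR_C24 is mismatched in BID only; AR_C24 in QD, AR_C12 and the AUC ratios are unaffected.

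This should be fixed before unblinding, but it concerns exploratory PK outputs and not the primary safety evaluation.

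**What to change.** 1. Define Dose in SAP 10.6.2 as dose per administration.
2. For Cmax,ss, C12,ss and C24,ss, add a BID/QD term or fit the power model within one regimen. Pool only AUC0-TAU,ss across regimens. If cohort 1 is the only BID cohort, the term absorbs it and the slope comes from the QD cohorts.
3. If only cohorts 1 and 2 complete, label the concentration ratios as a BID versus QD comparison and draw no dose-proportionality conclusion. Report the AUC0-TAU,ss ratio as a CL/F comparison confounded with regimen.
4. Limit AR_C24 to QD and use AR_C12 and AR_AUC0-12 for BID. Record this in SAP section 12, because the protocol lists AR_C24 without restriction.
5. If a later cohort is dosed fed, which Protocol 3.1, 3.3 and 5.4 allow, state that food is confounded with dose in the slope. A regimen term does not remove this. As an assumption only, a fed/fasted ratio of 1.2 in a single later QD cohort at twice the dose gives a slope of 1 + ln 1.2/ln 2 = 1.26.
6. Reconcile Protocol 5.3 with Protocol Table 2 on the regimen of cohorts 3 and 4.

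**Cost.** SAP and protocol wording plus PK programming; no new samples. The slope interval widens slightly. With three cohorts and CV 30%, σ = √ln 1.09 = 0.294. The 90% half-width goes from 1.746 × 0.294/√(4(ln 2)²) = 0.37 (16 df) to 1.753 × 0.294/√(3(ln 2)²) = 0.43 (15 df). The average over simulated trials with the regimen term is 0.42.

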
 • To assess endpoints related to TMP-301 mechanism of action • To evaluate CYP1A2 genotypes and their association with phenotypes for potential impact on metabolism and to identify biomarkers of potential response to TMP-301. 	
Accumulation ratio derived as:
 
 • $AR_{AUC_{0-12}} = AUC_{0-12,ss} / AUC_{0-12, Day 1}$ • $AR_{AUC_{0-24}} = AUC_{0-24,ss} / AUC_{0-24, Day 1}$ • $AR_{C_{max}} = C_{max,ss} / C_{max,FD, Day 1}$ • $AR_{C_{12}} = C_{12,ss} / C_{12, Day 1}$ • $AR_{C_{24}} = C_{24,ss} / C_{24, Day 1}$ • Estimations of dose proportionality at steady State. Dose-normalized PK parameters (C_{max}, C_{12}, C_{24}, and AUC_{0-12} and AUC_{0-24}, when appropriate) will be assessed graphically for dose-proportionality For BID cohorts, $AUC_{0-TAU,ss} = AUC_{0-12,ss}$, For QD cohorts, $AUC_{0-TAU,ss} = AUC_{0-24,ss}$ • Estimation of time to achieve steady state (C_{trough} will be displayed graphically and summarized descriptively by day to assess for steady state) • As a marker of CYP1A2 activity, the ratio of paraxanthine to caffeine concentration (at 4 hours post caffeine dose) will be reported on Day -1 and Day 14. Change in CYP1A2 activity will be derived as $CYP1A2_ratio = \frac{\text{paraxanthine/caffeine concentration day 14}}{\text{paraxanthine/caffeine concentration day -1}}$
--	---

Abbreviations: AE = adverse event; ECG = electrocardiogram; PK = pharmacokinetics

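### SAP 10.6.2 treats a slope 90% CI that includes 1 as evidence of dose proportionality, but it shows only that slope = 1 was not rejected

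*SAP*

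**What the plan says.** SAP 10.6.2 fits a power model to four log-transformed steady-state parameters (Cmax, C12, C24 and AUC over the dosing interval), with ln(dose) as a continuous effect. For the model's estimate it states: "A point estimate and a 90% confidence interval will be derived for the slope". It then adds the decision rule: a parameter can be "considered to be dose-proportional if the 90% CIs for the slope coefficient that include 1 will suggest evidence of dose proportionality". It gives no acceptance limits for the slope, no maximum CI width and no precision target.

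The same section replaces the power model with a geometric mean ratio and 90% CI on dose-normalised parameters when only two cohorts are completed. Its reference to at least three doses sits in the sentence on sub-ranges of dose. SAP 10.6.1 adds that dose-normalised parameters "will be assessed graphically for dose-proportionality", without a criterion.

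On the design, SAP 3.1 states "Each cohort will consist of 8 subjects (6:2 for active: placebo"). Cohort 1 is "Group 1 (6 subjects): 50 mg of TMP-301 bid", cohort 2 is "Group 3 (6 subjects): 50 mg of TMP-301 qd", and cohort 3 is "Group 5 (6 subjects): Dose regimen of TMP-301 to be determined"; cohort 4 is equally open. SAP Table 2 marks cohorts 3 and 4 as optional. SAP Table 1 lists "Estimations of dose proportionality at steady State" with the exploratory objectives.

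**The concern.** The event that the 90% CI includes 1 is the same as the event that the hypothesis slope = 1 is not rejected at two-sided 10%. Failure to reject is not evidence for the hypothesis. The rule therefore runs the wrong way: the wider the CI, the easier it is to earn the label.

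SAP 3.5 reports no formal sample size calculation, and each dose has 6 active subjects, so an imprecise slope is a realistic prospect. What is at stake is a prespecified statement in the study report that exposure is dose-proportional when the data may be compatible with a material departure from it.

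**Working it through.** The plan states no power, margin or precision figure for the slope, so there is nothing of its own to reproduce. The check is of how the rule behaves.

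**Inputs from the documents:** 6 active subjects per cohort (SAP 3.1); 90% CI, linear model in ln(dose), label given if the CI includes 1 (SAP 10.6.2).

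**Assumptions, not in the documents:** three distinct doses of one regimen; dose sets 50/75/100, 50/100/150 and 50/100/200 mg, chosen only for arithmetic; between-subject CV of 20, 30, 40 or 60%; log-normal errors. Under the current cohorts, three doses of one regimen starting from cohort 2 would need both optional cohorts at new once-daily doses, with cohort 1 left out. The SAP does not say that cohort 1 would be left out.

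**Formulas.** With r the ratio of highest to lowest dose and f the true fold change in dose-normalised exposure across that range:

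- SD on the log scale: s = sqrt(ln(1 + CV²))
- SE(slope) = s / sqrt(Sxx), with Sxx = Σ(ln D − mean ln D)² over 18 subjects
- true slope = 1 + ln(f)/ln(r)
- P(label) = P(|T| ≤ 1.746), with T noncentral t on 16 df and noncentrality (slope − 1)/SE

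**Worked case:** 50/100/200 mg, CV 40%, f = 1.5.

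- Sxx = 6 × (0.693² + 0 + 0.693²) = 5.765, square root 2.401
- s = sqrt(ln 1.16) = 0.385, so SE = 0.385/2.401 = 0.160
- true slope = 1 + 0.405/1.386 = 1.292, so noncentrality = 0.292/0.160 = 1.82
- P(label) = 46.0%

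**Chance that a true 1.5-fold change is labelled proportional:**

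| Doses (mg) | r | True slope | CV 20% | CV 30% | CV 40% | CV 60% |
|---|---|---|---|---|---|---|
| 50/75/100 | 2 | 1.58 | 3.9% | 25.6% | 45.6% | 66.3% |
| 50/100/150 | 3 | 1.37 | 3.7% | 25.1% | 45.2% | 66.0% |
| 50/100/200 | 4 | 1.29 | 4.0% | 26.0% | 46.0% | 66.5% |

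Expressed as a fold change, the answer hardly depends on the dose set. A 2-fold change gives about 0, 1, 9 and 33%. A 1.5-fold fall gives the same values as a 1.5-fold rise. If the slope is exactly 1, the label is given 90% of the time at any CV.

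**Effect of precision.** For 50/100/200 mg, CV 40% and a true slope of 1.3 (4^0.3 = 1.52-fold), the label is given 67% of the time with 3 subjects per dose, 44% with 6, 17% with 12 and 2% with 24. Fewer data make the false label more likely.

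**Observed changes that still pass.** The CI half-width is 1.746 × SE. In the worked case it is 0.280, and 4^0.280 = 1.47. Taking the sample SD equal to the assumed SD, an observed change of up to about 1.22, 1.34, 1.47 and 1.74-fold at CV 20, 30, 40 and 60% still earns the label, for all three dose sets to within rounding.

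**The case against.** The strongest reply is that little hangs on this sentence. Dose proportionality is exploratory. The protocol asks for a graphical assessment, and SAP 10.6.1 keeps it. The slope and its CI are reported whatever the label, so a careful reader can see an imprecise result. The wording is hedged. Escalation is bounded by tolerability and by the AUC and Cmax limits in Protocol 3.1, not by this label. If neither optional cohort runs, the rule is never used. The prior PK sections of the protocol are redacted, so the sponsor may hold variability data that make the problem small. All of this stands and limits the consequence. It does not make the inference correct: even hedged, the sentence attaches evidence of proportionality to a non-significant test.

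Four stronger readings are tempting, and the documents do not support them.

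- A reader might infer that the trial is likely to mislabel its results. The CV and the cohort 3 and 4 doses are not given, and at CV 20% a 1.5-fold change is mislabelled only about 4% of the time.
- A reader might extend the calculation to four cohorts by entering cohort 1 as 100 mg/day. SAP Table 7 defines AUC over the dosing interval as AUC0-12 for bid, so under linear PK cohort 1 reflects one 50 mg dose. With assumed doses 50/100/150/200 mg, that coding gives an expected slope of 1.065 even when PK is exactly linear. Figures built on it do not describe this design for that parameter.
- A reader might take three distinct doses as the stated trigger. The text names two completed cohorts as the trigger for the fallback and mentions three doses only for sub-ranges.
- A reader might charge the two-cohort branch with the same fault. That branch reports a ratio and CI and attaches no verdict to them.

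**Conclusion.** The rule is wrong as written, and no other passage repairs it. This rests on what a confidence interval means and needs no assumed figure. Its size is conditional: with three doses of one regimen and 6 active subjects each, the risk of a false label for a 1.5-fold change is small at CV 20% and considerable at CV 40 to 60%. Whether a given fold change matters depends on a margin that the documents do not set. The consequence is confined to how an exploratory PK result is described. Safety conclusions and dose escalation are not affected. It should be corrected because the conclusion would otherwise carry prespecified status.

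**What to change.** Delete the sentence in SAP 10.6.2 and replace it with: *The slope and its 90% CI will be reported as estimates. A 90% CI that includes 1 does not establish dose proportionality.* Optionally, add the implied dose-normalised change r^(slope − 1) with its 90% CI, where r is the ratio of highest to lowest dose. This is a matter of presentation, since the slope CI and the doses already determine it.

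If a pass/fail statement is kept, require the whole 90% CI to lie within prespecified, justified limits tied to r, and report the result as inconclusive otherwise.

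The cost is one sentence and no new data. The change should be made before database lock and unblinding, because SAP section 5 treats later analyses as post hoc. The downside is that a proportionality claim will seldom be possible with 6 per dose. Taking 0.80 to 1.25 as illustrative limits, the slope bounds are 1 ± ln(1.25)/ln(r), or 0.839 to 1.161 for r = 4. By simulation under exact proportionality with three doses, these would be met about 21, 1 and 0% of the time at CV 20, 30 and 40%. Estimation without a verdict is therefore the realistic choice.
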